Electric shocks are one of the most efficient ways to induce anxiety in the laboratory. The shocks will be delivered through two disk electrodes located on the forearm or on two fingers.

Test shocks

At the beginning of the study a shock workup procedure is conducted to determine the setting for the overall procedure for each subject. The level of shock is initially set at 3.5 μ Amp (the low range). A shock is administered and the subject is asked to rate it on a scale from 1 (not at all painful) to 5 (extremely painful). We then increase the level of shock slightly until the subject identifies the sensation at a rating level of 4. No more than three test shocks are given and the level is selected based on the subjective ratings provided by the participant. No subject will ever receive a shock rated more than 4 for the duration of their study. In addition, subjects are reminded that they have the opportunity to withdraw from the study at anytime if they wish.

Participant rating of the experience:

```
CNS IRB Protocol Template (rev. 9-21-11)
```

At the end of the study subjects are asked to retrospectively rate the shock experiment on a scale from 1 (not at all painful) to 10 (extremely painful). This provides us with an assessment of the overall unpleasantness of the experience during the entire shock experiment.

Electric shock: sural nerve

The shock will be administered on the sural nerve in the retromalleolar space and recording of the response from the biceps femoris muscle. The aim is to have an objective measure of unpleasantness. The R3 reflex will be evoked using a method similar to that described in Rhudy et al (2005). Briefly, electric stimulation of the sural nerve will be four to six rectangular wave pulses of 1- to 2-ms duration every 2 to 5 ms. A trial will begin with 0 mA and increased in 1.0-1.5-mA steps until a R3 reflex is detected. Stimulus intensity will then be decreased in 0.75 mA steps until a reflex is no longer detected. This up–down staircase procedure will be repeated two more times, but with 0.5-mA steps until the R3 threshold is determined. Once the R3 threshold is determined, the intensity of stimulation during experiments in which we used shock to evoke anxiety will be set at 1.2 times the threshold intensity. At this intensity, subjects usually report a slightly painful pin-prick sensation (Rhudy et al 2005).

e. End of Participation

The participant is discharged following each experiment. Subjects will be terminated from the protocol if they request to discontinue participation.

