Brief Description: This study aimed to understand the influence of acute physical exercise on the interaction between anxiety and cognition. The study had a within-subjects design and took place over three outpatient study visits, one exercise screening visit and two study visits, each separated by five to eight days. During one visit, the participant will pedal lightly on the stationary bicycle for 30 minutes. During the other visit, the participant will pedal on the exercise bicycle at a moderate intensity, ensured by levels of resistance and defined by target heart rate of resting heart rate plus 60-70% of her heart rate reserve. Then, after completion of the exercise, participants will perform an N-back task under threat of shock and safe conditions to measure working memory (Vytal, Cornwell, Letkiewicz, Arkin, & Grillon, 2013). After 15 minutes (10 min break, 5 min startle habituation), participants will undergo the NPU task under threat of shock and safe conditions to measure physiological response to fear and anxiety (Schmitz & Grillon, 2012).

Outcome: Exercise has been proposed as a first line of treatment for anxiety disorders. We examined potential mechanisms that may be responsible for the anxiolytic effect of anxiety. A first study investigated whether exercise affected fear and anxiety differentially. Results showed that biking at 60-70% of heart rate reserve for 30 min reduced anxiety evoked by unpredictable shock but not fear evoked by predictable shock (Lago et al, in press). These results suggest that exercise therapeutic effect may involve specific modulation of the anxiety and not the fear system. A second study examined whether exercise anxiolytic effect was mediated by improved cognitive control. Two observations motivated this study. First, engagement of attention control during increased working memory (WM) load can decrease anxiety. Second, exercise can improve attention control. Therefore, we hypothesized that exercise would boost the anxiolytic effects of increased WM load via its strengthening of attention control. Anxiety was induced by threat of shock and was quantified with anxiety-potentiated startle (APS) (Lago et al, in press). Subjects were tested after two types of activity, exercise (biking at 60-70% of heart rate reserve) and control-activity (biking at 10-20% of heart rate reserve). After each activity, participants completed a WM task (n-back) at low- and

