4. STUDY DESIGN AND METHODS

a) Study overview

This protocol examines the interaction between cognition and induced anxiety. This study consists of the following sub-studies. Subjects can enroll in one or more sub-studies. They will sign a consent form for each sub-study. These sub-studies require 1 outpatient visit to the Clinical Center for up to 4 hours or up to two visits if it includes a telehealth consenting visit.

Study A: Working memory and anxietyStudy C: Effect of anxiety on sustained attention to response task (SART)Study D: Effect of anxiety on Stroop task (closed for accrual; data analysis only)Study E: Pilot studiesStudy F: Pilot study of sural nerve stimulation

b) Recruitment

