This study will examine whether greater WM capacity or practice is associated with increased or decreased anxiety during performance of a WM task during threat of shock. On the one hand, increase in WM capacity could be associated with more ability to allocate resources to anxious thoughts, therefore increasing anxiety. On the other hand, better WM reflects better ability to screen out intrusive stimuli and thoughts, thereby decreasing anxiety. As for task practice, we hypothesize that practice will make more resources available to allocate to anxious thoughts.

Subjects will be asked to remember verbal and nonverbal stimuli. These stimuli consist of words, pictures, letters or spatial locations in series of stimuli. Participants will be instructed to remember one, two, or three stimuli back from the current stimulus on the screen (n-back task). There will be 2 groups. One group will practice the N-back task

minimally (e.g., 5 min) and the other group will have more extensive training (e.g., 20 min).

Sub-study C: Effect of anxiety on sustained attention to response task (SART)

SART are sustained attention tasks during which a button-press response is made to frequent targets and responses are withheld to rare non targets. SART have been used extensively to study inattention, "off-task thinking", task-unrelated thoughts, and 'mind wandering" (Robertson, Manly et al. 1997). An advantage of this task is that it enables us to identify periods when the mind wanders. When the mind wanders, subjects make errors of commitment (they button-press to non-targets). We will use SART to attempt to identify periods of anxious thoughts.

Subjects will have to respond to frequent targets (e.g., digits 1, 2, 3...) and to withhold response to rare non targets (e.g., 3). We will examine the association between response speed and anxiety as assessed with startle. Mind wandering in SART is associated with faster RT. We will examine whether faster RT is associated with larger potentiated startle. We will also probe subjects' thoughts (on-task, off-task, anxious thoughts) after each startle stimulus to assess whether anxious thoughts predict startle potentiation.

Sub-study D: Effect of anxiety on Stroop task

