• Sensory/Perceptual processing: We will examine the effect of threat of shock on the ability to remain focused on goal-relevant stimuli in the presence of potentially interfering distractors. We will use a response-competition paradigm during which subjects make speeded responses indicating whether a central target is one of two pre-specified targets while attempting to ignore peripheral distractors (Lavie 2005). Slower responses in the presence of an incongruent distractor will be compared with a congruent distractor. Perceptual load is manipulated by varying the number of items that are similar to the target. **Conflict tasks:** Tasks such as the Flanker task will be used. This task requires subjects to attend to a centrally presented stimulus and ignore the flanking stimuli surrounding it. When the flanking stimuli are mapped to the opposite response from the center stimulus (incompatible trials), subjects respond more slowly because of the need to exercise top-down control. We are interested in this task because it examines top-down control without relying on working memory. Executive function/cognitive flexibility: We will examine threat of shock on complex executive functions testing including decision making (e.g., Iowa Gambling task), planning ability (e.g., Tower of London), set-shifting (e.g., Wisconsin Card Sorting test), and solving tasks (e.g., anagrams). **Working memory**: We have found that threat of shock reduced performance on n-back WM tasks. Because of the nature of N-back tasks, it is unclear whether reduced performance is due to anxiety interference with memory or other processes such as perception, encoding, or retrieval. We will investigate whether we can dissociate the effect of anxiety on these processes using Sternberg WM tasks.

Sub-study F: Pilot studies of sural nerve stimulation

In Protocol 01-M-0185, the shocks are delivered via electrodes located on the forearm or fingers. In order to obtain an objective measure of unpleasantness, we will pilot a new technique using up to 30 subjects in a session lasting up to 2 hours.

This pilot experiment will be conducted under the supervision of the PI, who used this technique when he was a graduate student.

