10. STATISTICAL ANALYSIS

The accrual ceiling for this protocol is 1575 healthy controls. The overall current target N for the protocol is 148 healthy controls.

Sub-study A (previously Study 2a)36 subjectsSub-study C (previously Study 2c)34 subjectsSub-study E (previously Study 2e)48 subjectsSub-study F (previously Study 2f)30 subjects

Study 2a: Working memory and anxiety

Analysis of the data: Startle and performance data will be analyzed with ANOVAs with repeated measures using condition (threat, safe) x Load (low, high). Power analysis: Based on pilot and published works in our lab, we expect an small/moderate effect size for startle potentiation (Cohen's d=0.3). A priori calculations indicate that the testing of 30 participants at an alpha of 0.05 would provide power of 0.80 to detect a significant 2 (Condition) x 2 (Load) interaction on startle response. Assuming a 20% attrition rate, we will collect (about) 36 subjects.

Study 2c: Effect of anxiety on sustained attention to response task (SART)

Analysis of the data: The main analysis is to compare startle magnitude when subjects focus on the task and when their mind wander with ANOVAs with repeated measures using condition (threat, safe) x thought (on task, off task).

Power analysis: Based on pilot works in our lab, we expect an small/moderate effect size for startle potentiation (Cohen's d=0.4). A priori calculations indicate that the testing of 28 participants at an alpha of 0.05 would provide power of 0.80 to detect a significant 2 (Condition) x 2 (Load) interaction on startle response. Assuming a 20% attrition rate, we will collect (about) 34 subjects.

Study 2d: Effect of anxiety on Stroop task

Study is 2d is is closed for accrual. We are currently analyzing the data.

Study 2e: Pilot studies

These pilot experiments are designed to determine the parameter of stimulation of study that will be used in our neuroimaging, psychopharmacological, and clinical studies conducted in our other protocols (03-M-0093, 02-M-0321, 02-M-0263). We use tasks in 4 domains, 1) sensory processing, 2) conflict, 3) executive function, and 4) working memory. We will use 12 subjects per domain for a total of 48 subjects.

Study 2f: Pilot study of sural nerve stimulation

This pilot study investigates the location of the stimulating and recording electrodes and different types of stimulus delivery. We have requested 30 subjects.

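### Sub-study A sets up two n-back practice groups, but the planned analysis pools them, their assignment is not described, and earlier n-back practice is not controlled at entry

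*Combined protocol and SAP*

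**What the plan says.** Section 4.d, Sub-study A, describes two groups. One practises the n-back "minimally (e.g., 5 min) and the other group will have more extensive training (e.g., 20 min"). The purpose of the split is stated: "As for task practice, we hypothesize that practice will make more resources available to allocate to anxious thoughts". The section does not say how a volunteer comes to be in one group or the other.

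Section 10, under Study 2a, gives the whole analysis plan for this sub-study: "Startle and performance data will be analyzed with ANOVAs with repeated measures using condition (threat, safe) x Load (low, high"). The sample size is tied to the interaction of those two factors, where "the testing of 30 participants at an alpha of 0.05 would provide power of 0.80", and 36 are to be enrolled. Practice group appears neither in the model nor in the power statement.

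On entry, section 4.a says "Subjects can enroll in one or more sub-studies" and gives no rule on earlier task exposure. The exclusion list in 3.c covers language, pregnancy, medical, psychiatric and substance history, medication, toxicology and NIMH employment. It has no item on having done the task before.

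The n-back was used in completed Study 2g (section 1): "After each activity, participants completed a WM task (n-back) at low- and" high load. Among the sub-studies listed in 4.a, only A names the n-back.

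**The concern.** A design with two practice groups and a practice hypothesis needs three things: a model term that compares the groups, an assignment method that makes them comparable, and some control over how practised people are on arrival. The plan states none of them.

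The first gap matters most. A model with Condition and Load only returns the average threat and load effects over both groups. It cannot say whether 20 minutes of practice changes anxiety relative to 5, so the sub-study would finish without a planned answer to one of its own questions.

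The third gap bears on the same contrast. The planned difference between the groups is about 20 - 5 = 15 minutes. Someone who has already done the n-back and is placed in the minimal-practice group is not minimally practised. If such volunteers fall evenly in both groups, the contrast shrinks. If assignment is not random and they gather in one group, the contrast is biased. With the method unstated, neither the direction nor the size of that bias can be worked out.

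**Working it through.** **1. The plan's own figure.** The inputs in section 10 (Study 2a) are d = 0.3, alpha 0.05 and n = 30. A 2 x 2 within-subject interaction is a one-sample t-test on each subject's contrast score. Taking d as the standardised contrast, the noncentrality is 0.3 x √30 = 1.64 on 29 df, which gives power 0.355 two-sided (0.484 one-sided), not 0.80. A power of 0.802 is reached if d is read as a simple paired difference with an unstated correlation of 0.84, since 0.3/√(2 x 0.16) = 0.53. That is a separate matter. What counts here is that the figure, on any reading, is for Condition x Load and says nothing about practice group.

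**2. What the practice contrast would need.** The hypothesis concerns anxiety under threat, so the natural test is Group x Condition on startle. That is a two-sample t-test on each subject's threat-minus-safe score. Assume the 30 analysed subjects split 15/15 (the plan gives no split) and a two-sided alpha of 0.05. The noncentrality is d x √(15/2) = 2.739 d on 28 df. Power reaches 0.80 at d = 1.06 (noncentrality 2.90). With 18 per group, if all 36 were analysed, it is d = 0.96. For scale, a between-group d of 0.3 (the plan's value for startle potentiation, not a practice effect) gives power 0.125 at 15 per group.

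**3. What earlier practice would do.** Let q be the share of volunteers whose earlier practice removes the group difference, spread evenly over both groups. The expected contrast is then (1 - q) x d. The documents give no value for q, so the rows below are assumptions. They start from a contrast that has 80% power when undiluted.

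| q (of 30 analysed) | effective d | noncentrality | power |
|---|---|---|---|
| 0 | 1.06 | 2.90 | 0.80 |
| 10% (3) | 0.954 | 2.61 | 0.71 |
| 20% (6) | 0.848 | 2.32 | 0.61 |
| 30% (9) | 0.742 | 2.03 | 0.50 |

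The sample size needed grows by 1/(1 - q)²: 1.23, 1.56 and 2.04 times for the last three rows. If a returner loses only part of the difference, q scales down in proportion.

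**4. Where practised volunteers could come from.** Study 2g had its participants do the n-back after each of two activities. It is complete, it is not on the list in 4.a, and neither its size nor any overlap with Sub-study A is given. Nothing in 3.c or 4.a keeps its volunteers out. Sub-study C uses the SART, and D (Stroop) is closed to accrual. The working-memory domain of E uses another task: "We will investigate whether we can dissociate the effect of anxiety on these processes using Sternberg WM tasks". A subgroup of F, of unstated size, does a working-memory or vigilance task that is not named.

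**5. What is untouched.** Condition and Load vary within each subject, so earlier practice is the same on both sides of every comparison in the planned test. It may change the average effect, but it does not confound it.

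**The case against.** The strongest reply is that no planned result is affected. Section 10 plans and powers only Condition x Load, which earlier practice does not confound, and a contrast needing d of about 1.06 would not be rescued by tighter entry rules. Most of this stands, and it limits the priority. It does not remove the first gap: the hypothesis and the two groups are in section 4.d, and section 10 has no analysis for them.

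A second reply is that the overlap may be zero. It may, and then nothing is lost. That can be known only if earlier sessions are recorded.

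Three stronger readings are tempting, and the documents do not support them:

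- A reader might infer from 4.a that joining several sub-studies itself sends practised volunteers into A. No open sub-study other than A is documented to use the n-back. E and F would matter only if practice transfers between tasks, and the documents do not address transfer.
- A reader might take Sub-study E's working-memory subjects ("We will use 12 subjects per domain for a total of 48 subjects") as an upper limit on returners, 12/36 or one third of A. That figure leaves out F's subgroup and Study 2g, both of unstated size, and assumes full transfer, so it bounds nothing.
- A reader might conclude that A must always come first. That would only move any carry-over to later sub-studies, including E's working-memory pilot.

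**Conclusion.** The point holds in this form. As written, section 10 cannot test the practice hypothesis of Sub-study A, the method of assigning the practice groups is not stated, and earlier n-back practice under this protocol is neither barred nor recorded by any stated rule. The missing model term is certain from the text. Dilution or bias from earlier practice is a possibility whose size is unknown: it may be nil, and the figures above show only how quickly power would fall if it were not. The detectable difference of about d = 1.06 rests on an assumed 15/15 split and a two-sided test. The Condition x Load result is not put in doubt by this point. Because the affected contrast is unpowered and the overlap unknown, priority is low to moderate.

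**What to change.** - **Section 10, Study 2a:** add practice group as a between-subject factor with its interactions with Condition and Load, and name the term that tests the hypothesis (Group x Condition on startle is the natural one). State that this contrast is not powered, with the detectable difference of about d = 1.06 at 15 per group, and that it will be reported as an estimate with a confidence interval.
- **Section 4.d, Sub-study A:** state that the practice groups are assigned at random, and in what ratio.
- **Entry to Sub-study A (3.c or 4.a):** record any earlier n-back session under this protocol, Study 2g included. Then either exclude on it, or balance the random assignment on it and adjust for it. The adjustment must include prior exposure's interaction with Condition, because a main effect alone does not adjust a threat-minus-safe difference.

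No fixed order of sub-studies is needed.

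The cost is small: a few sentences, an assignment list and a check of earlier enrolment. The group factor takes one error degree of freedom from the Condition x Load test (30 - 1 = 29 becomes 30 - 2 = 28). The exclusion option makes the recruitment pool for A slightly smaller, and the alternative adds a few model terms.

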 - Anxiety Sensitivity Index (Peterson and Reiss 1992)
 - Beck Anxiety Inventory (Beck and Steer 1987)
 - Beck Depression Inventory (BDI) (Beck and Steer 1987)
 - Fear Questionnaire (Marks and Mathews 1979)
 - Penn State Worry Questionnaire (Meyer, Miller et al. 1990)
 - Positive and Negative Affectivity Scale PANAS (Watson, Clark et al. 1988)
 - Multidimensional Personality Questionnaire Harm Avoidance (MPQ-HA) (Tellegen 2002)
 - Mood and Anxiety Symptoms Questionnaire (MASQ) short-Form (Keogh and Reidy 2000)

- Adverse Life Event Checklist (Gray, Litz et al. 2004)
- Attention Control Scale (Derryberry and Reed 2002)

The non-analogue measures from these reports may be completed by the participant on the Clinical Trial Survey System (CTSS) online system. Subjects will have signed the 01-M-0254 screening consent prior to filling out these measures on CTSS. AIs may then collect data from the Clinical Trials Database (CTDB) for the purposes of this study. Participants may enter their responses while at NIH using a wireless-device interface to access the NIH-intranet secure CTDB. Two items will require real time monitoring. Item #9 on the Beck Depression Inventory (BDI) and item #61 on the Mood and Anxiety Symptom Questionnaire-Short Form (MASQ-SF) inquire about suicidality. An associate investigator must check both items before the participant leaves the Clinical Center. If the participant indicates anything higher than a "0" ("I don't have thoughts of killing myself") on the BDI item #9 or a "1" ("not at all") on the MASQ-SF item #61, the associate investigator must notify a staff clinician. The staff clinician must assess for immediate safety and refer the participant to appropriate resources. If the screening protocol (01-M-0254) finds them to be eligible, they will undergo the informed consent process for 01-M-0185.

d) Study procedures

Procedures for the separate studies are outlined below.

Anxiety will be induced with the threat of shock.

• The threat of shock experiment requires a single session. Performance of cognitive tasks will be conducted during alternating periods of shock threat and safety.

Sub-study A: Working memory and anxiety

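### Sub-study C compares on-task with off-task startle without a time-in-session term, although thought state is observed rather than assigned and startle may habituate

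*Combined protocol and SAP*

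**What the plan says.** Section 4.d describes the design shared by the threat-of-shock sub-studies: "The threat of shock experiment requires a single session" and "Performance of cognitive tasks will be conducted during alternating periods of shock threat and safety". It does not state the starting condition, the number of blocks or any counterbalancing.

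For sub-study C, Section 4.d says how thought state is obtained: "We will also probe subjects' thoughts (on-task, off-task, anxious thoughts) after each startle stimulus". Section 10 (Study 2c) says the main analysis is to "compare startle magnitude when subjects focus on the task and when their mind wander", using the factors "condition (threat, safe) x thought (on task, off task").

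For sub-study A, Section 10 (Study 2a) says "Startle and performance data will be analyzed with ANOVAs with repeated measures using condition (threat, safe) x Load (low, high").

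Neither model has a term for time, block, probe number or order.

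The one sign in the documents that startle habituates is in Section 1, completed Study 2g: "After 15 minutes (10 min break, 5 min startle habituation") before the threat task. The startle procedure common to the current sub-studies (Section 4) describes no such run.

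**The concern.** Threat and safe are set by the experimenter, so alternating them keeps their average times in the session close together. Thought state is set by the subject. Whatever governs when the mind wanders also governs when the off-task startles are collected. If startle falls during the session and off-task reports become more frequent, the off-task mean is built from later and smaller responses. The ANOVA then attributes the effect of time to Thought.

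At stake is the comparison that Section 10 names as C's main analysis. The direction matters too. Section 4.d links mind wandering to faster responses and asks whether faster responses go with larger potentiated startle. The artefact makes off-task startle look smaller, so it could hide or reverse such a pattern. A null or reversed Thought effect would then be hard to interpret.

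**Working it through.** **Inputs from the documents.** C has 28 evaluable subjects (Section 10), a single session, alternating conditions, a thought probe after each startle, and a Condition x Thought model. The documents give no habituation rate, number of probes or time course of off-task reports, so the plan has no figure of its own to reproduce on this point. C's stated power of 0.80 is a separate matter.

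**Assumptions, shown as ranges.** Startle falls linearly by D = 0.5, 1.0 or 1.5 probe-level SDs over the session, equally under threat and safe. The probability of an off-task report is flat, or rises linearly by b. There are 32 probes, the starting condition is random, and there is no true thought effect.

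**Expected bias.** Scale session time u from 0 to 1. The off-task minus on-task difference in mean time is b x Var(u) / [p(1 - p)], where p is the average off-task rate. For 32 equally spaced probes, Var(u) = 33/(12 x 31) = 0.0887. The startle bias is -D times that difference.

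- Rate 0.2 to 0.5: b = 0.3, p = 0.35. 0.3 x 0.0887/(0.35 x 0.65) = 0.117. Bias -0.06, -0.12, -0.18 SD for the three values of D.
- Rate 0.3 to 0.7: b = 0.4, p = 0.5. 0.4 x 0.0887/0.25 = 0.142. Bias -0.07, -0.14, -0.21 SD.
- Flat rate: b = 0, so the bias is 0.

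**Simulation** (n = 28, 400 runs per setting; Monte Carlo standard error about 0.011 at a true rate of 0.05 and 0.025 at 0.5). Cells give results for D = 0.5 / 1.0 / 1.5.

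| Off-task rate, both conditions | Simulated bias (SD) | Type I error for Thought, as planned | With a time term |
|---|---|---|---|
| Flat 0.3 | 0.00 / 0.00 / -0.01 | 0.06 / 0.05 / 0.06 | 0.03 / 0.05 / 0.05 |
| 0.2 to 0.5 | -0.05 / -0.12 / -0.17 | 0.11 / 0.30 / 0.54 | 0.04 / 0.06 / 0.05 |
| 0.3 to 0.7 | -0.07 / -0.14 / -0.21 | 0.20 / 0.49 / 0.77 | 0.04 / 0.05 / 0.07 |

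The simulated bias agrees with the formula. With 24 probes instead of 32, the 0.2-to-0.5 row gives type I error of 0.10 / 0.27 / 0.49, again restored by a time term (to about 0.04) with almost no loss of precision.

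**Interaction in C.** When the off-task trend is the same under threat and safe, type I error for Condition x Thought stays at 0.04 to 0.09. When the rate rises from 0.3 to 0.7 under safe and stays flat under threat, it is 0.09 / 0.16 / 0.28.

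**Sub-study A, only if every subject starts with the same condition.** With K alternating blocks and a linear fall of D from first to last block mean, the starting condition is favoured by D/(K - 1). For D = 1 that is 1/3 = 0.33 SD with 4 blocks and 1/7 = 0.14 SD with 8. The shift is the same at both loads, so the bias in Condition x Load is 0. It becomes non-zero only if load is also blocked in fixed order and the decline is curved: for an exponential decline with D = 1, 0.58 SD with 4 blocks and 0.21 SD with 8.

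**The case against.** The strongest reply is that the two trends producing the bias are not in the documents. Nothing says that off-task reports increase during the session. The 5-minute run in Study 2g came before its task, so it shows that the group allows for habituation but not how far startle falls during C. This stands: the sizes above are conditional, and a flat off-task rate removes the problem.

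A reader might infer more in three ways.

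- *That A's threat-safe difference is biased because one condition always comes first.* The documents say only that the periods alternate, and the text for sub-study E names safe before threat. An unstated start order is missing detail, not evidence of a fixed order. Even a fixed order would shift mainly the Condition main effect, not the interaction on which A is powered.
- *That the artefact would manufacture the pattern C is looking for.* It runs the other way.
- *That C's interaction is generally biased.* With an equal startle decline in both conditions, it is biased only if the off-task trend differs between threat and safe, and nothing in the documents suggests that it does. If the Section 4.d question about potentiated startle is read strictly as threat minus safe, it falls under this narrower condition.

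It is also fair to say that a probe-number covariate cannot simply be added to an ANOVA on each subject's cell means. The remedy changes the model.

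None of this answers the point that Thought is unassigned and that C's named main contrast has no protection against a shared time trend.

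**Conclusion.** The point holds for sub-study C, conditionally. The planned on-task versus off-task comparison is open to confounding with time in session, and counterbalancing threat and safe cannot remove it. If off-task reports rise from 0.2 to 0.5 while startle falls by 0.5 to 1.5 SD, the contrast is biased downward by about 0.05 to 0.17 SD, and type I error is about 0.10 to 0.5 instead of 0.05. If the off-task rate is flat there is no bias. The rise, the size of the decline and the number of probes are all assumptions. For A the documents support only a request to state the order. This is an inexpensive improvement worth making before C is analysed; it does not show that the design is unsound.

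**What to change.** **Sub-study C.** Analyse startle at probe level with a linear mixed model: a subject random effect; Condition, Thought and their product; plus centred probe number and probe number x Condition. The last term lets the decline differ between threat and safe. Report the off-task rate by probe number and condition, so that a reader can see whether the adjustment mattered.

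**Sub-study A.** State the starting order. If it is not already counterbalanced, start half of each practice group with threat and half with safe. Under a linear decline the order effect then averages out across subjects.

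**Cost.** In C, a probe-level model replaces the ANOVA on cell means, with one or two extra parameters. In A, at most a start-order list. No new data, procedures or subjects are needed.
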